#### 5.2 Non-inclusion criteria

The patients who comply with at least one of the criteria listed below will not be included:

- 1. Prior tonsillectomy, tonsillotomy.
- 2. Chronic conditions of the nasopharynx or oropharynx, ulcerative oral disorders.
- 3. History of hypersensitivity or allergic reactions to any components of the study drugs or local anesthetics.
- 4. Use of analgesics during less than 12 hours before the trial start and/or impossibility to discontinue the analgesics for the trial period.

- 5. Use of antibiotics during less than 48 hours before the trial start and/or planned use of antibiotics during the trial.
- 6. Use of topical drugs (aerosols, gargle solutions, fast-disintegrating tablets/lozenges/pastilles) in the pharynx during less than 12 hours before the trial start and/or impossibility to discontinue topical drugs, except for the study drugs, for the trial period.
- 7. Use of the systemic, inhalation, or nasal glucocorticosteroids during 30 days before the trial start and/or planned use of the glucocorticosteroids (except for the topical skin drugs) during the trial.
- 8. Impossibility to discontinue other drugs which might influence the trial results, e.g. antiviral or prohibited concomitant drugs (see *Prohibited concomitant therapy* section), for the trial period.
- 9. Signs of a primary bacterial pharyngitis or secondary bacterial infection (including body temperature increase above 37.5 °C, purulent pharyngeal pellicles, significant intoxication, leukocytosis, neutrocytosis, WBC differential's shift to the left (increase in stab neutrophils, presence of younger neutrophils), ESR more than 30 mm/h).
- 10. Granular pharyngitis.
- 11. Signs of rhinitis, sinusitis, otitis, eustachitis, laryngitis, tracheitis, bronchitis (such conditions require therapy which might influence the trial results).
- 12. Phenylketonuria.
- 13. Deficit of saccharase or isomaltase (according to anamnesis data).
- 14. Glucose-galactose malabsorption (according to anamnesis data).
- 15. Fructose intolerance.
- 16. Diabetes mellitus.
- 17. Glucose-6-phosphate dehydrogenase deficiency (according to anamnesis data).
- 18. Hemochromatosis.
- 19. Anemia (Hb less than 120 g/l according to hematology test).
- 20. Hyperoxaluria.
- 21. Urolithiasis.
- 22. Myasthenia.
- 23. Severe, uncontrolled, cardiovascular condition which, in the Investigator's opinion, preclude the patient from participation in the trial, namely:

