# 9.1.4 Safety parameters analysis

A descriptive part of the safety analysis will include an evaluation of incidences and two-sided CI 95% for the following parameters in every trial group:

- AEs: the incidence in total and for separate categories (according to MedDRA), for the trial and by groups;
- SAEs: the incidence in total and for separate categories (according to MedDRA), for the trial and by groups;
- Incidence of clinically significant changes of the physical examination results by visits and groups;
- Incidence of clinically significant changes of the laboratory results by visits and groups;
- Incidence of clinically significant changes of the vital signs (body temperature, BP, pulse rate, HR) by visits and groups;
- Incidence of clinically significant changes of the ECG parameters by visits and groups;
- Global tolerance evaluation during the trial by the Investigator and patient;

The Fisher's exact test will be used to compare incidences between the groups, and chi-square will be used to compare the global therapy tolerability by the Investigator and patient. The McNemar's test will be used to evaluate for the dynamic changes during the trial (before–after) for all the repeatedly evaluated incidences in every group.

In addition to the incidence, all the quantitative safety parameters will be presented in a table form (laboratory data, vital signs, ECG) by visits and groups. The difference will be evaluated using 2-way-ANOVA (group and visit numbers will serve as the relevant factors). The post-hoc criteria will be used in case of significant difference.

Safety analysis will be performed on the safety population.

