# 3.8 Acceptable deadlines for visits and a scope of investigations

The data obtained at Visit 1 (Day 1) will be considered to be the initial data for the endpoint analysis.

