# 4.1.5 Analysis of laboratory and functional tests results

A between group comparison of the vital signs changes (systolic blood pressure, diastolic blood pressure, breathing rate, heart rate, body temperature) revealed at every visit (Visits 1, 2, 3) as well as laboratory results and ECG changes incidence obtained at Visit 1 and Visits 2–3 is envisaged. In addition, significance of the changes will be evaluated for all repeatedly measured parameters.

The following laboratory parameters will be reviewed:

- Hematology
  - o Hemoglobin
  - o RBC
  - o ESR
  - o WBC
  - o Neutrophils
    - Juvenile
    - Stab
    - Segmented
  - o Eosinophils
  - o Basophils
  - o Monocytes
  - o Lymphocytes
- Biochemistry
  - o Total protein
  - o AST
  - o ALT
  - o Total bilirubin

ANOVA methods will be used to reveal a simultaneous influence of a group and time factors on the quantitative parameters.

The cross tables analysis will be used to reveal a correlation between the qualitative parameters (chi-squared test).

For the quantitative parameters, a comparison will be made by Student's t-test for the independent samples (in case of confirmation of hypothesis on normal variables distribution) or Mann–Whitney test (in case of rejection of hypothesis on normal variables distribution); for the qualitative parameters—using Fisher's exact test.

To evaluate significance of the intragroup changes during the trial for repeatedly measured parameters, the paired Student's t-test (in case of confirmation of hypothesis on normal variables distribution) or paired Wilcoxon signed-rank test (in case of rejection of hypothesis on normal variables distribution) will be used; for the qualitative parameters McNemar's test will be used.

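### Within-arm before-after safety tests can show worsening without any drug effect where the entry rules bar abnormal values at Visit 1, which is also the baseline

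*Protocol*

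**What the plan says.** **Within-arm tests.** Protocol 9.1.4: "The McNemar's test will be used to evaluate for the dynamic changes during the trial (before–after) for all the repeatedly evaluated incidences in every group". SAP 4.1.5 keeps this for binary items ("for the qualitative parameters McNemar's test will be used") and adds a test for quantitative ones: "To evaluate significance of the intragroup changes during the trial for repeatedly measured parameters, the paired Student's t-test", or the Wilcoxon signed-rank test if normality is rejected. The paired tests appear only in the SAP.

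**Baseline.** SAP 3.8: "The data obtained at Visit 1 (Day 1) will be considered to be the initial data for the endpoint analysis". Protocol 4.2.4.1 places haematology, vital signs, the eligibility decision and randomization in that same visit.

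**Entry limits.** Inclusion criterion 6 (Protocol 5.1) requires an axillary temperature below 37.5 °C. Non-inclusion criterion 9 (Protocol 5.2) bars signs of bacterial infection, among them "leukocytosis, neutrocytosis, WBC differential's shift to the left" and "ESR more than 30 mm/h". Criterion 19 bars haemoglobin below 120 g/l. Each limit acts on one side only. The criteria set no numeric limit for total protein, ALT, AST, bilirubin, heart rate or breathing rate.

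**Between-arm tests.** Protocol 9.1.4 also plans Fisher's exact test between arms and a two-way ANOVA with group and visit. SAP 4.1.5 plans between-arm comparison of vital signs, laboratory results and ECG. Safety tests are two-sided at 0.05 (Protocol 9.3, SAP 3.10). SAP 4 gives safety variables an exploratory role and plans no multiplicity correction.

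**The concern.** McNemar's null hypothesis is that changes from normal to abnormal and from abnormal to normal are equally likely. If an abnormal value at Visit 1 keeps a patient out, the second kind of change hardly exists among those enrolled. Ordinary day-to-day variation then produces changes in one direction only, and the null is false whatever the drug does. SAP Tables 12 and 13 count haematology results as within reference or deviating at each visit, which is the natural input to such a test.

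The paired t and Wilcoxon tests meet a related difficulty. Cutting the baseline distribution on one side causes regression to the mean, while an acute illness resolves over the same days. In the source trial, 36.9% of placebo patients had no sore throat on Day 4 (Protocol 9.2, Table 2). A change over time within one arm therefore says little about the drug.

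At stake is a report showing significant laboratory or temperature worsening that comes from selection. It could also be significant in one arm and not in the other by chance, and be taken for a difference between the drugs. The safety goals in Protocol 3.2 are comparative.

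**Working it through.** The documents give no figure for these tests, so there is none to reproduce. Arm size comes from Protocol 9.2: 140 randomized and 128 completed per arm. Level: 0.05 two-sided, hence 2.5% nominal in the worsening direction.

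**Step 1: smallest count that rejects.** With b new abnormal values and none resolving, the exact two-sided McNemar p is 2 × 0.5^b.
- b = 5: 2/32 = 0.063.
- b = 6: 2/64 = 0.031.
- The continuity-corrected form also rejects at b = 6: (6 − 1)²/6 = 4.17, p = 0.041.
- The uncorrected form rejects at b = 4: 4²/4 = 4.0, p = 0.046.

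**Step 2: chance of reaching six.** With 140 patients, all normal at baseline, and a Day 4 abnormal rate q, P(6 or more) is 6% at q = 2%, 71% at q = 5% and 99.6% at q = 10%.

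**Step 3: what q selection alone produces.** Let f be the share of unselected patients beyond the limit and ρ the correlation between Visit 1 and Day 4. Neither is in the documents, so both are assumed over a range. With no drug effect and no time trend,

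q = [f − P(beyond the limit at both visits)] / (1 − f).

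Results from 4,000 simulated trials per setting: bivariate normal values, baseline cut at the limit, abnormality limit equal to the entry limit, 140 per arm. Entries are for ρ = 0.9 / 0.7 / 0.5.

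| f | q (%) | McNemar worsening (%) | Paired t worsening (%) |
|---|---|---|---|
| 2.5% | 1.0 / 1.7 / 2.1 | 0.2 / 3 / 7 | 3 / 5 / 6 |
| 5% | 1.9 / 3.2 / 3.9 | 5 / 30 / 48 | 4 / 7 / 10 |
| 10% | 3.5 / 5.9 / 7.5 | 35 / 85 / 95 | 8 / 15 / 22 |
| 20% | 6.3 / 11.0 / 14.2 | 88 / 99.9 / 100 | 15 / 38 / 58 |

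Cross-check: the binomial tail at q = 7.5% is 95.6%, against 95% simulated at f = 10%, ρ = 0.5. With 128 per arm the f = 10% row for McNemar is 28 / 78 / 92%.

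**Step 4: is selection the cause?** Without the entry cut (f = 10%), McNemar worsening is 0.9–1.8% and paired t 2.1–2.5%.

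**Step 5: resolving illness (ρ = 0.7).** Entries are for f = 5 / 10 / 20%.
- Mean falls by 0.2 SD: paired t shows worsening in 0.1% or less and improvement in 73 / 59 / 32%; McNemar worsening is 5 / 40 / 93%.
- Mean falls by 0.5 SD: McNemar worsening is 0.1 / 2.5 / 30.5%.

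**Step 6: abnormality flagged well inside the entry cut.** This could apply to ESR. With 20–30% flagged and only the top 2.5–5% cut, McNemar worsening is 1.6–3.4%.

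**Step 7: between-arm tests on the same selected data (3,000 runs).** At f/ρ = 5%/0.7, 10%/0.5 and 20%/0.5, Fisher's test rejects in 1.5, 2.4 and 3.8% of trials, and a t-test on change in 4.8, 4.2 and 5.1%.

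**Step 8: one arm only.** At f = 5%, ρ = 0.7, each arm rejects in 30% of trials. With independent arms, exactly one does so in 2 × 0.30 × 0.70 = 42%.

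**The case against.** The strongest reply is that the valid analysis is already planned. Both documents compare the arms directly, Step 7 shows those comparisons hold their level, and no text ties a safety conclusion to a within-arm p-value or proposes to set one arm's p-value against the other's. This stands, and it limits the weight of the point.

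A reader might infer that these tests will signal worsening. The documents do not support that. They give neither the share excluded nor the correlation, and Step 3 includes settings with no excess. The high rates need a sizeable share of patients beyond a single limit.

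A reader might also infer that every safety parameter is affected. Several have no entry limit. The ESR and haemoglobin cuts are entry rules that nothing in the documents equates with the site laboratories' reference limits, so deviating baseline values may remain. In addition, the incidences in Protocol 9.1.4 are of clinically significant changes, judged by the investigator (SAP 3.6). These may be rarer than the threshold crossings simulated here.

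Finally, a reader might expect the paired t-test to lean towards worsening. That shift is modest unless many patients are excluded, and Step 5 shows that resolving inflammation can reverse it. What remains is that its direction is unsettled and its result cannot be attributed to the drug.

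**Conclusion.** The point holds in limited form. For items whose abnormal values are barred at Visit 1, McNemar's null is false by design. This is clearest for WBC, neutrophils, left shift and temperature; it extends to ESR and haemoglobin only if the abnormality limit equals the entry cut. Under the assumed inputs at 140 per arm, false worsening in an arm ranges from no excess (f = 2.5%, ρ = 0.9) to 35–95% (f = 10%, ρ = 0.9 to 0.5), against a nominal 2.5%. These rates assume normally distributed values, equal entry and abnormality limits and no time trend; a strong resolving trend lowers them. The within-arm paired t and Wilcoxon tests mix regression to the mean with recovery and cannot be read as a drug effect in either direction.

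This is a modest correction to the safety analysis. It does not show that the trial's safety comparison is invalid.

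**What to change.** - **Remove** the McNemar sentence from Protocol 9.1.4 and the intragroup tests from SAP 4.1.5, at minimum for WBC, neutrophils, left shift, temperature, ESR and haemoglobin.
- **Show** within-arm change descriptively: normal/abnormal shift tables and mean change by visit, with a note that Visit 1 values are truncated by the entry criteria.
- **Rest safety inference** on the between-arm comparison already planned. Add a 95% CI for the risk difference in abnormal values and a baseline-adjusted mean difference for quantitative parameters.
- **State the timing**: Group B patients who have not recovered by Day 4 have their laboratory tests and ECG on Day 5 (Protocol 4.2.4.2 and 4.2.4.3), so the last on-treatment comparison includes a one-day difference for them.

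The cost is wording in two sections and the loss of within-arm p-values that some readers expect. No new data are needed.

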# 4.2.2 Trial design flowchart

# 4.2.3 Trial procedures

# 4.2.3.1 Trial procedures in a table form

#### Table 1. Visit schedule

Trial period	Screening/Randomization/Therapy initiation	Treatment		Further follow-up 	Unscheduled visits
Visits	Visit 1	Visit 2  Visit 3 		Visit 4	
Day after initiation of therapy	Day 1	Day 4 Day 5		Day 6/7	
Trial procedures					
Signing of the Informed Consent Form	•				
Demographic data (date of birth, sex, age)	•				
Measurement of weight and height	•				
Medical history	•				
Collection of complaints, actualization of anamnesis	•	•	•		•
Records on the concomitant therapy	•	•	•		•
Evaluation of the throat pain intensity according to VAS by a patient	•	•	•		
Fill-in of TSS questionnaire 	•	•	•		•
Physical examination (including topical examination)	•	•	•		•
Measurement of vital signs 	•	• *	•		•
Hematology 	•	• *	•		
Biochemistry 	•	• *	•		
Urine pregnancy test 	•				
12-lead ECG	•	• *	•		
Evaluation of inclusion/non-inclusion criteria	•				

<sup>1 A follow up visit will be held in the form of a phone contact with the patient to reveal the possible AEs.

<sup>2 In case of premature discontinuation, the follow-up procedures are the same as those at Visit 2.

<sup>3 Only for the Group B patients who did not meet the recovery criteria (total  $TSS \le 2$ ) at Visit 2 (Day 4) and continued the therapy.

<sup>4 Fill-in of TSS questionnaire by the Investigator (scores for every question should be summarized to obtain a total TSS score).

<sup>5 Systolic blood pressure (mm Hg), diastolic blood pressure (mm Hg), breathing rate (per minute), pulse rate (beats per minute), axillary body temperature (°C).

<sup>6 Hb, RBC, WBC with differential, ESR—at the trial site laboratory.

<sup>7 Total protein, AST, ALT, total bilirubin.

<sup>8 For women with the preserved childbearing potential only.

Trial period	Screening/rand omization/ther apy initiation	Treatment		Further follow-up 	Unscheduled visits
Visits	Visit 1	Visit 2 	Visit 3 	Visit 4	
Day after initiation of therapy	Day 1	Day 4	Day 5	Day 6/7	
Trial procedures					
Randomization	•				
Dispensing of the study drugs	•				
Dispensing of the patient's diaries	•				

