Return of the unused study drugs		• *	•		
Return of the patient's diaries		• *	•		
Evaluation of adverse events (including based on results of the throat and pharynx examination during the trial site visits)	•	•	•	•	•
Evaluation of exclusion criteria		•	•		•
Global evaluation of therapy tolerability by the patient and the physician		• *	•		•
Compliance evaluation (diary completion, administration of the study drugs)		•	•		•

Notes:

\* Only for Group A patients and those Group B patients who achieved the recovery criteria (total TSS score  $\leq 2$ ).

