# 4.2.4.3 Trial completion visit for Group B patients (Visit 3, Day 5)

This visit is for Group B patients only (ANTI-ANGIN® FORMULA) who did not achieve the recovery criteria (total TSS  $\leq$  2) at Visit 2 (Day 4)

Visit 3 is conducted on Day 5; the patient must visit the trial site in the fasted state and bring the filled-in diary and unused drug.

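### The two-way ANOVA for quantitative safety parameters specifies no patient term, and the visit scheme makes its between-arm comparisons depend on recovery status; one end-of-treatment value per patient avoids both problems

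*Protocol*

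**What the plan says.** Protocol 9.1.4 tabulates laboratory data, vital signs and ECG by visit and group, and then states: "The difference will be evaluated using 2-way-ANOVA (group and visit numbers will serve as the relevant factors"). A significant result leads to post-hoc tests. SAP 4.1.5 keeps the method: "ANOVA methods will be used to reveal a simultaneous influence of a group and time factors on the quantitative parameters". Neither text mentions a patient effect, a repeated-measures form or a covariance structure.

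SAP 4.1.5 also plans between-group tests (Student's t or Mann–Whitney) and within-group tests: "To evaluate significance of the intragroup changes during the trial for repeatedly measured parameters, the paired Student's t-test", with a Wilcoxon alternative. It describes the laboratory and ECG comparison as "laboratory results and ECG changes incidence obtained at Visit 1 and Visits 2–3 is envisaged" but does not define what Visits 2–3 means. The SAP shells for hematology and biochemistry (Tables 9 to 11) list Visits 1, 2 and 3 and carry a p row.

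The visit scheme differs by arm and by outcome. Of Visit 3, Protocol 4.2.4.3 says: "This visit is for Group B patients only". Footnote 3 to Table 1 narrows it further: "Only for the Group B patients who did not meet the recovery criteria" at Visit 2. Hematology, biochemistry and ECG at Visit 2 carry an asterisk in Table 1, explained as "Only for Group A patients and those Group B patients who achieved the recovery criteria".

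**The concern.** There are two separate defects.

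First, an ordinary two-way ANOVA on group and visit assumes independent observations. Values from one patient at two visits are normally correlated. Ignoring this makes the group p-values too small and the p-values for contrasts within patients, such as group-by-visit, too large.

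Second, visit number does not mean the same thing in the two arms. At Visit 3 there is no Angal patient at all. At Visit 2, for laboratory values and ECG, every Angal patient is set against the comparator patients who did well. If a parameter differs between recovered and unrecovered patients, the arms will differ on it without any drug effect. The link is plausible from the protocol itself: body temperature is a TSS item, and non-inclusion criterion 9 treats leukocytosis and a raised ESR as signs of bacterial infection.

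At stake is whether the report shows spurious differences between arms in laboratory, ECG or vital-sign values, or misses small real ones. Protocol 9.2 names safety alongside efficacy in the statistical objective, so these p-values will be read.

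**Working it through.** The documents give no figure for this analysis beyond the two-sided 0.05 threshold in Protocol 9.3, so there is nothing of theirs to reproduce.

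**Step 1. Who contributes values** (Protocol Table 1, 4.2.4.2 and 4.2.4.3)

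| | Visit 1 | Visit 2 | Visit 3 |
|---|---|---|---|
| Labs and ECG, Group A | all | all | none |
| Labs and ECG, Group B | all | recovered only | unrecovered only |
| Vital signs, Group A | all | all | none |
| Vital signs, Group B | all | all (4.2.4.2) or recovered only (Table 1 asterisk) | unrecovered only |

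Labs and ECG are therefore scheduled twice per patient; only vital signs can reach three.

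**Step 2. Missing patient term alone.** Assume two complete visits and within-patient correlation ρ. The true variance of the group contrast is (1+ρ) times what the ANOVA assumes; for group-by-visit it is (1−ρ) times. Hence:

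- group test error = 2[1 − Φ(1.96/√(1+ρ))]
- group-by-visit error = 2[1 − Φ(1.96/√(1−ρ))]
- group-by-visit power, where a correct test has 80% = Φ(2.80 − 1.96/√(1−ρ)), with 2.80 = 1.96 + 0.84

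| ρ (assumed) | 1.96/√(1+ρ) | Group error | 1.96/√(1−ρ) | Group-by-visit error | Power against 80% |
|---|---|---|---|---|---|
| 0.3 | 1.72 | 8.6% | 2.34 | 1.9% | 68% |
| 0.5 | 1.60 | 11.0% | 2.77 | 0.6% | 51% |
| 0.7 | 1.50 | 13.3% | 3.58 | 0.03% | 22% |

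**Step 3. Empty cell.** With two groups and three visits, the full group-by-visit model has 6 columns, but only 5 cells hold data, so its rank is 5. The Visit 3 interaction cannot be estimated. A patient term does not change this.

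**Step 4. Actual visit pattern.** Simulation with no treatment effect, 140 per arm (Protocol 9.2) and 2,000 runs per scenario, so the standard error near 5% is √(0.05×0.95/2000) ≈ 0.5 points. The share unrecovered at Day 4 (equal in both arms), the shift in unrecovered patients and ρ are assumptions.

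- Lab/ECG pattern, 37% unrecovered, no shift: group test 9.9%, 12.2% and 15.2% at ρ = 0.5, 0.7 and 0.9.
- Lab/ECG pattern, 20% to 50% unrecovered, shift 0.5 SD: group test 13% to 26% at ρ = 0.5 to 0.9, and still 7% to 18% at ρ = 0, where only the selection is at work.
- A plain Visit 2 lab comparison between arms, same shift, ρ = 0 to 0.9: 11% to 40%.
- Vital-sign pattern with everyone measured at Visit 2: group test 10% to 17% at ρ = 0.5 to 0.9; a plain Visit 2 comparison stays at 4% to 6%.

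**Step 5. The remedy under the same scenarios.** One end-of-treatment value per patient, ANCOVA on arm and Visit 1 value: 3.8% to 6.0%, nominal within simulation error. The simulation assumed no Day 4 to Day 5 change.

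**The case against.** The independence assumption is inferred. Protocol 9.1 calls its account brief, and the SAP says only ANOVA methods, in a section that recognises repeated measurement and uses paired tests. A repeated-measures ANOVA is not excluded. This stands: the text supports saying that no patient term is specified, not that its omission was intended. It answers Step 2 only; the empty cell and the recovery-dependent sampling remain.

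The SAP's between-group t or Mann–Whitney tests use one value per patient if applied visit by visit, so correlation does not affect them. This also stands, but for labs and ECG at Visit 2 they carry the same selection on outcome (Step 4, third line).

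The SAP's Visits 2–3 wording, with Protocol 4.2.3.2.6 and 4.2.3.2.7 placing the second blood sample and ECG at Visit 2 or 3, can be read as a single post-treatment point. That is close to the remedy. But it is undefined, and the table shells list three visits.

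A reader might infer from the very low group-by-visit error rates that this test has almost no power. That does not follow. With 140 per arm and a difference in change of 0.5 SD (assumed), it has 88%, 92% and 97% power at ρ = 0.3, 0.5 and 0.7, against 94%, 99% and nearly 100% for a correct test. The loss matters mainly for smaller effects, and neither document says that an interaction will be fitted.

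Finally, SAP section 4 gives safety variables an exploratory role. That limits the weight of the point.

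**Conclusion.** The point holds in two parts. As written, the ANOVA has no patient term, and the group test then has a true error of about 8.6% to 13.3% for ρ between 0.3 and 0.7. Those figures rest on an assumed correlation and two complete visits, and they lapse if a repeated-measures form was intended. The second part depends on neither assumption: the Group A by Visit 3 cell is empty, and for labs and ECG the Visit 2 comparison is selected on outcome. How far the selection distorts a p-value depends on how strongly a parameter is tied to recovery, which the documents do not give.

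A reader might infer that the trial's safety conclusions as a whole are unsound. The documents do not support that. The primary non-inferiority test, the adverse-event comparisons and the incidence of clinically significant changes do not use this ANOVA. The severity is modest: it should be corrected before analysis, but it does not threaten the main result.

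**What to change.** Replace the two-way ANOVA in Protocol 9.1.4 and SAP 4.1.5.

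- Define Visits 2–3 in SAP 4.1.5 as one end-of-treatment value per patient: Visit 2 for Group A and recovered Group B patients, Visit 3 for the other Group B patients.
- For each quantitative parameter, compare arms by ANCOVA on arm and the Visit 1 value. Alternatively, use a mixed model with a patient effect and baseline versus end of treatment as the time factor.
- Use the same end-of-treatment value in the SAP's between-group laboratory tests. Report Visit 3 values on their own descriptively, without a between-arm p-value, and adjust the table shells to match.
- Reconcile Visit 2 vital signs: Protocol 4.2.4.2 lists them for both groups, whereas Table 1 marks them with the restricting asterisk. If they are measured in everyone, use Visit 2 for all patients.

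One limitation should be stated in the SAP: the end-of-treatment value is Day 5 for unrecovered Group B patients and Day 4 for everyone else, so the comparison assumes little change between those days.

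The cost is wording and a standard model in R, with no new data or visits. Because the SAP says it makes no changes to the protocol, the change also needs an amendment or a justified entry under Protocol 9.6, made before the final analysis.
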